9.5.3 Exploratory analysis

Inferential analysis will not be performed if the smallest group involving in the comparison has a size smaller than 10.

To explore the long term efficacy of FeetMe home-based rehabilitation program compared to conventional physiotherapy in patients who continue to Week 24, the following will be applied:

The change in gait velocity and Stance Time Variability from baseline to week 24 will be compared between the Feetme group and the conventional rehabilitation group using the constrained longitudinal data analysis (cLDA) model or a non-parametric analysis of covariance in case of violation of the assumption of cLDA model, as indicated for the primary objective. The change in these 2 parameters from week 12 to week 24 will be compared using the linear mixed model with an adjustment on the value at week 12 and on the covariable used in the stratified randomisation "conventional physiotherapy in progress". In this model, the centre will be included as a random effect. The rate of falls assessed within 24 weeks will be compared between the two groups using the generalized linear model (GLM with log link function and negative binomial distribution) with the logarithm of duration of patient's follow up (censored at week 24) as offset variable.

All other endpoints will be analysed using descriptive statistics:

- To explore the maintenance of the effect after 3 months in patients who stop physiotherapy at Week 12, the method described previously will be employed for the analysis of the first exploratory objective, namely inferential analysis for the three parameters gait velocity, stance time variability and rate of falls and descriptive analyses for the other endpoints.
- To explore the efficacy in patients who switch from one treatment to the other at Week 12, descriptive analyses will be performed.

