	Change from baseline to Week 12 (Visit 3) in Stance Time Variability assessed during the 6MWT.
	Secondary Endpoints
	• Rate of falls at Week 12 based on the results of the falls diary.
	• Change from baseline to Week 12 (Visit 3) in the asymmetry of the swing duration assessed during the 6MWT.
	• Change from baseline to Week 12 (Visit 3) in the Mini-BESTest.
	• Change from baseline to Week 12 (Visit 3) in Unified Parkinson's Disease Rating Scale (MDS-UPDRS) Part III sub-score.
	• Change from baseline to Week 12 (Visit 3) in the results of the Parkinson Disease Questionnaire (PDQ-39).
	Exploratory Endpoints
	• Rate of falls at Week 24 based on the results of the falls diary.
	• Change from Baseline to Week 24 (Visit 4) and from Week 12 (Visit 3) to Week 24 in:
	- Gait velocity (cm/s) assessed during the 6MWT
	- Stance Time Variability assessed during the 6MWT
	- Asymmetry of the swing duration assessed during 6MWT
	- the Mini-BESTest
	- MDS-UPDRS Part III sub-score
	- the results of the PDQ-39
	 Change from Baseline to Week 12 (Visit 3) and to Week 24 (Visit 4) and from Week 12 to Week 24 in the:
	- gait parameters measured by the FeetMe Monitor during the 6MWTs other than ones of the primary and secondary endpoints
	- gait parameters measured by the FeetMe Monitor during remote gait monitoring
	- results of the pain VAS
	- results of the Parkinson Disease Sleep Scale 2 (PDSS2)
	- results of the Clinical and Patient Global Impression of Severity scales (CGI/PGI-S)
	- results of the Clinical and Patient Global Impression of Improvement scales (CGI/PGI-I)
	• results of the MDS-UPDRS I, II and IV sub scores
	• Actual versus prescribed time spent on physiotherapy at Week 12 and Week 24.
· · · · · · · · · · · · · · · · · · ·	

	• Results of the Patient and Investigator satisfaction questionnaire.
	• Number of device and protocol procedure related adverse events at Week 12 and at Week 24.

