5 STUDY OBJECTIVES AND ENDPOINTS

Table 5.1 Study Objectives and Endpoints

Primary Objective	Primary Endpoints				
To evaluate the efficacy of FeetMe home-based rehabilitation program compared to conventional physiotherapy at Week 12 in PD patients assessed by gait velocity.	Change from baseline to Week 12 (Visit 3) in gait velocity (cm/s) assessed during the 6 Minutes Walk Test (6MWT).				
Key Secondary Objective	Key Secondary Endpoint				
To evaluate the efficacy of FeetMe home-based rehabilitation program compared to conventional physiotherapy at Week 12 in PD patients assessed by stance time variability.	Change from baseline to Week 12 (Visit 3) in Stance Time Variability assessed during the 6 Minutes Walk Test (6MWT).				
Secondary Objectives	Secondary Endpoints				
To evaluate the efficacy of FeetMe home-based rehabilitation program compared to conventional physiotherapy at Week 12 in PD patients assessed	• Rate of falls at Week 12 (Visit 3) based on the results of the falls diary.				
 by: rate of falls standard gait and balance exercises 	• Change from baseline to Week 12 (Visit 3) in the asymmetry of the swing duration assessed during the 6 Minutes Walk Test (6MWT).				
MDS-UPDRS Part IIIquality of life	• Change from baseline to Week 12 (Visit 3) in the MiniBESTest.				
	• Change from baseline to Week 12 (Visit 3) in MDS-UPDRS part III sub-score.				
	• Change from baseline to Week 12 (Visit 3) the results of the Parkinson Disease Questionnaire (PDQ-39)				
Exploratory Objectives	Exploratory Endpoints				

• To explore the long term efficacy home-based rehabilitation program to conventional physiotherapy in pa	of FeetMe compared atients who	Rate of falls at Week 24 based on the results of the falls diary. Change from Baseline to Week 24 (Visit 4)
continue to Week 24		and from Week 12 (Visit 3) to Week 24 in:
• To explore the maintenance of the 3 months in patients who stop phy at Week 12.	effect after vsiotherapy	- Gait velocity (cm/s) assessed during the 6MWT
 To explore the efficacy in patients of from one treatment to the other at X 	who switch Veek 12	- Stance Time Variability assessed during the 6MWT
	V CCR 12.	- Asymmetry of the swing duration assessed during 6MWT
		- the Mini-BESTest
		- MDS-UPDRS Part III sub-score
		- the results of the PDQ-39
	•	Change from Baseline to Week 12 (Visit 3) and to Week 24 (Visit 4) and from Week 12 to Week 24 in the:

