
9.5.2 Analysis for the secondary endpoints

The statistical method described for the primary objective will be used for the analysis of the following secondary endpoints:

- Change from baseline to Week 12 (Visit 3) in Stance Time Variability assessed during the 6 Minutes Walk Test (6MWT).
- Change from baseline to Week 12 (Visit 3) in the asymmetry of the swing duration assessed during the 6 Minutes Walk Test (6MWT).
- Change from baseline to Week 12 (Visit 3) in the MiniBESTest.
- Change from baseline to Week 12 (Visit 3) in MDS-UPDRS part III sub-score.
- Change from baseline to Week 12 (Visit 3) the results of the Parkinson Disease Questionnaire (PDQ-39)

The rate of falls during the primary intervention period will be compared between the 2 groups using a generalized linear model (GLM with log link function and negative binomial distribution) with the logarithm of duration of patient's follow up (censored at week 12) as offset variable. Effect size will be estimated by the relative risk ((Feetme rehabilitation versus conventional rehabilitation) and it's 95% confidence interval from the using GLM model.

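### The 0–24 week falls rate in Section 9.5.3 cannot show whether a falls benefit is maintained in patients who stop at Week 12

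*Protocol*

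**What the plan says.** At Visit 3 each patient chooses to continue, switch or stop (protocol Sections 6.1 and 7.5).

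- **Endpoint lists.** The Synopsis and Table 5.1 give one later falls endpoint: "Rate of falls at Week 24 based on the results of the falls diary". The next item, covering gait velocity, stance time variability, swing asymmetry, Mini-BESTest, MDS-UPDRS Part III and PDQ-39, is introduced by "Change from Baseline to Week 24 (Visit 4) and from Week 12 (Visit 3) to Week 24 in". Falls are not in that list.
- **Week 12 falls analysis, Section 9.5.2.** "The rate of falls during the primary intervention period will be compared between the 2 groups", by a negative binomial model with follow-up censored at week 12.
- **Later falls analysis, Section 9.5.3.** Under the long-term objective in patients who continue, the plan says "The rate of falls assessed within 24 weeks will be compared between the two groups using the generalized linear model", fitted "with the logarithm of duration of patient's follow up (censored at week 24) as offset variable".
- **Second-period analysis, Section 9.5.3.** "The change in these 2 parameters from week 12 to week 24 will be compared using the linear mixed model". The two parameters are gait velocity and stance time variability.
- **Maintenance in stoppers, Section 9.5.3.** The plan reuses the method of the first exploratory objective, "namely inferential analysis for the three parameters gait velocity, stance time variability and rate of falls".
- **Switchers, Section 9.5.3.** Descriptive analyses only.

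**The concern.** Whether an effect is maintained after stopping is a question about the time after Visit 3. The falls rate assigned to that question counts events from the start of the study. A reduction earned wholly during the first 12 weeks therefore stays in the estimate, whatever happens afterwards.

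At stake is the reading of the result: a 24-week rate ratio below 1 among stoppers could be reported as a lasting effect when the benefit had already gone. Section 4.2.2 gives falls a central place in the rationale, so such a reading would carry weight even from an exploratory analysis.

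**Working it through.** **Inputs.** The counting window and offset come from Section 9.5.3 and the choice at Visit 3 from Sections 6.1 and 7.5. The protocol states no falls rate, falls ratio or dispersion, so every such value below is an assumption. The only design figure it computes is the gait velocity sample size (60 per group, 75 after 20% dropout). That figure reproduces, but this point does not rest on it.

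**Step 1: which window applies.** The Week 12 model covers the primary intervention period, censored at week 12. The later model has the same form, censored at week 24, and no start at week 12 is given. The natural reading is a count over weeks 0–24. With complete follow-up, the share before stopping is 12/24 = one half.

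**Step 2: what the 24-week ratio measures.** Let RR1 and RR2 be the falls rate ratios (FeetMe versus conventional) in weeks 0–12 and 12–24. Let f be the control falls rate in weeks 12–24 divided by that in weeks 0–12. With equal follow-up in both halves:

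RR(0–24) = (RR1 + f × RR2) / (1 + f)

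With a constant control rate, f = 1:

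- Maintained, 0.75 then 0.75: (0.75 + 0.75)/2 = 0.75
- Lost, 0.50 then 1.00: (0.50 + 1.00)/2 = 0.75

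The two histories give the same value. A ratio counted over weeks 12–24 alone would be 0.75 in the first case and 1.00 in the second.

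**Step 3: a changing control rate.** For 0.50 then 1.00:

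| f | Calculation | 24-week ratio |
|---|---|---|
| 0.5 | (0.50 + 0.50)/1.5 | 0.67 |
| 1 | (0.50 + 1.00)/2 | 0.75 |
| 1.5 | (0.50 + 1.50)/2.5 | 0.80 |
| 2 | (0.50 + 2.00)/3 | 0.83 |

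The lost benefit still shows as a reduction throughout this range.

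**Step 4: behaviour of the test.** A gamma-Poisson simulation used 2,000 runs per case, f = 1 and a two-group negative binomial Wald test with dispersion taken as known. It assumed 30 or 60 patients per group, 0.5 or 2 control falls per 12 weeks, and dispersion 1 or 2.

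| | Maintained (0.75, 0.75) | Lost (0.50, 1.00) |
|---|---|---|
| Weeks 0–24: rejection | 8.6% to 28.4% | 8.6% to 29.7% |
| Weeks 0–24: median ratio | about 0.75 | about 0.75 |
| Weeks 12–24: rejection | 7.2% to 23.8% | 3.9% to 6.2% |
| Weeks 12–24: median ratio | about 0.75 | about 1.00 |

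The 24-week analysis does not tell the cases apart in estimate or in test. The weeks 12–24 rate does so in its estimate, although its rejection rate is also low.

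**The case against.** The strongest objection is that the 0–24 week falls model is written for continuers, and for them it is sound. Their treatment does not change at Visit 3, the objective is long-term efficacy, and a cumulative rate answers it much as the baseline-to-Week 24 gait change does. This stands.

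Three stronger readings are therefore tempting but not supported:

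- A reader might infer that the rate pools patients who continue, switch and stop. Section 9.5.3 treats them separately; what is mixed is two time periods within a group.
- A reader might infer that a planned model for switchers averages two treatments. Switchers get descriptive analyses only.
- A reader might count the reuse of weeks 0–12 falls as an error. Any cumulative endpoint contains its earlier part, and the testing hierarchy in Section 9.2.2 assigns no alpha here.

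Other points limit the weight of the issue. Section 6.1 calls the data after Week 12 exploratory, and Section 9.5.3 drops inference when the smallest group has fewer than 10 patients. Maintenance would also be judged on gait velocity and stance time variability, which do have a second-period comparison. A constant control rate is doubtful when both groups of stoppers have stopped; Step 3 varies it for that reason.

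Finally, the window for stoppers is not restated, and the analysis plan, which is not at hand, might set another. The protocol nevertheless fixes the window and offset once and says the same method is reused with falls named, so this is a stated choice and not merely a detail left open.

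**Conclusion.** The point holds for the maintenance objective in stoppers. As written, the falls analysis assigned to that objective cannot distinguish a benefit that lasted from one that disappeared at Week 12, and the protocol lists no Week 12 to 24 falls rate that could.

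The size is illustrative: the equal 24-week ratios, and the range over changing control rates, rest on assumed ratios and equal follow-up in both halves. The conclusion also rests on reading the stopper analysis as using the 0–24 week window, which is the natural reading of the text. It should be corrected, but it concerns one exploratory objective and bears on no primary, key secondary or secondary conclusion.

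**What to change.** Add to Section 9.5.3 and to the exploratory endpoint lists (Synopsis and Table 5.1) a falls rate from Visit 3 to Visit 4. Count diary events dated after Visit 3, with the log of follow-up time after Visit 3 as the offset.

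- Use this rate for the maintenance objective in stoppers.
- Report it descriptively for switchers, and beside the long-term comparison in continuers.
- Show the weeks 0–12 rate of the same patients next to it.
- Keep the 0–24 week rate as the cumulative long-term summary for continuers.
- Label these comparisons as non-randomised, because patients choose their group at Week 12. The new rate describes the second period; it does not by itself prove maintenance in a self-selected group.

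The cost is wording. The diary runs throughout participation (Section 8.7) and dates each event (Appendix G), so no new data are needed. The downside is fewer events per analysis and so less precision: in the simulated maintained case, rejection falls from 8.6%–28.4% to 7.2%–23.8%.

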10 DATA HANDLING

10.1 Data Monitoring Committee

No Data Monitoring Committee is planned for this study.

10.2 Gait Data Collection and Management

Gait Data are collected and processed internally by FeetMe according to Standard Operating Procedures on data management.

10.3 Clinical Data Collection and Monitoring

Clinical data – other than gait data – will be entered by the site into an electronic data capture system (EDC) by completing the eCRF via a secure internet connection. Data entered into the eCRF must be verifiable against the source documents at the study centre. Any changes to the data entered in the EDC will have an audit trail. Missing or inconsistent data will be queried via the system to the Investigator for clarification. Subsequent modifications to the database will be documented.

Monitoring of this study is the responsibility of the Sponsor and may be delegated to a CRO or a contract monitor. It is understood that the study Sponsor and/or its appointee will regularly contact the Investigator and conduct onsite visits at the study site with the purpose of maintaining compliance with this clinical investigational plan, GCP and all relevant regulatory requirements.

The Investigator agrees that the Sponsor and/or Sponsor-authorised personnel will be allowed to inspect all records pertinent with the study and to have direct access to patient files (provided that subject confidentiality is maintained, in accordance with local laws and regulations) with the aim of verifying eCRF entries, their completeness and clinical investigational plan compliance.

The Investigator also agrees to cooperate with the monitor's activities when requested and to coordinate with the monitor to ensure that any issue uncovered in the course of such visits are analysed and solved.

The Investigator agrees to supply the Sponsor with relevant original data from the clinical records or study documentation, especially in case doubts about data transcription should arise. Complete access to the study records is as well required in case of audit inspections and inquiries from competent national or local authorities, provided that confidentiality of the study patients is protected.

A clinical site monitoring plan, including all details about the monitoring strategy will be provided to the Investigator.

10.4 Record Retention

The Investigators will retain all study records for a minimum of 15 years after the conclusion of the study, or, alternatively, for a period of time meeting the local, regional, or national standards; whichever is greater. The Investigator will be responsible for maintaining adequate and accurate electronic or hard copy source documents of all observations and data generated during this trial including any data clarification forms received from the Sponsor. Such documentation is subject to inspection by the Sponsor and relevant regulatory authorities.

Before proceeding with the destruction of the study records or any study-related document, the Investigator must contact the Sponsor and receive explicit authorisation from the Sponsor to destroy such records. This notification must happen even if retention requirements have been met. A notification must be provided to the Sponsor prior to the transferring of any study records to another party or moving them to a new location.

Should the Investigator leave the clinical site of this study, a notification must be provided to the Sponsor in a timely manner, allowing for suitable arrangements to be made, aimed at ensuring the retainment of all study records and maintaining continuing access to the study records for the Sponsor and Regulatory authorities. Notice of such transfer will be given to the Sponsor in writing.

10.5 Reporting and Publication

The Sponsor will register this study and its results on a public online repository (e.g. Clinicaltrials.gov) regardless of the outcome, in accordance with the applicable laws.

All type(s) of publication (including presentations at scientific meetings) of any results derived from this study is only permitted if the publication is approved by the Sponsor. Published data must not compromise the objectives of the study. If the publication is initiated by the Investigator, s/he agrees to provide relative abstracts and manuscripts to the Sponsor prior to any submission activity. This has the purpose of protecting possible Sponsor's confidential or proprietary information and/or to allow the Sponsor to share information from other clinical studies which may be unknown to the Investigator. Investigators who do not qualify for authorship may be acknowledged in publications resulting from the trial. By agreeing to participate in the trial, Investigators consent to such acknowledgement in any publications resulting from its conduct.

All type(s) of publication of any results derived from this study is only permitted if the publication is approved by the Sponsor. Published data must not compromise the objectives of the study.

All information concerning this study which was not previously published is to be considered confidential property of the Sponsor and must not be disclosed without express consent.

The Sponsor is responsible for producing the clinical study report in compliance with ICH E3.

11 QUALITY ASSURANCE AND QUALITY CONTROL

Measures to ensure quality and completeness of the data will be implemented by the Sponsor, in order to assure that all data are reliable and have been correctly processed. The Sponsor, CRO and data management vendor will be responsible for the management of data for this study. The Investigator will be responsible for the correct recording of study data in the eCRF using the EDC system and for approving all eCRF data before final database lock.

Over the course of the study, as well as after completion, quality assurance officers appointed by the Sponsor or pertinent authorities may perform inspections and audits. The Investigator has the responsibility of cooperating and facilitating such inspections as well as to provide relevant documents if requested. In the event of discrepancies in data, the study site will be queried in order to resolve them through the EDC system.

12 ETHICS

12.1 Independent Ethics Committee or Institutional Review Board

The Sponsor must obtain approval of this clinical investigational plan and any relevant study material (e.g., ICF) from the Independent Ethics Committee before starting the study. Approval from the committee must be documented in writing, in the form of a letter to the study Sponsor before the study can start, specifying the date of approval.

Any modification to this clinical investigational plan or relevant study material after EC approval must be re-submitted by the Sponsor to the committee in accordance with local or national regulatory requirements.

12.2 Regulatory Authorities

Notifications and submissions to the appropriate regulatory Authorities will be executed as prescribed by national or local legislation in the country where this study is taking place.

12.3 Ethical Conduct of the Study

This study will comply and will be conducted in full conformance with the ICH E6 guideline for Good Clinical Practice, with the principles stated in the World Medical Association's Declaration of Helsinki, MDR 2017/745 and MPDG, ISO 14155, 2020 and all applicable local, regional, and national laws or regulations of the country in which the research is conducted.

12.4 Informed Consent

Prior to any data collection for this study, each subject will be informed in detail about the study device and the nature of the clinical investigation, with particular care given to any potential risks or discomforts to be expected by the subjects.

The Sponsor's Informed Consent Form (ICF) will be provided to the study site. The ICF will be provided in a certified translation of the local language.

It is the responsibility of the Investigator to obtain written subject informed consent from any subject considering participation in this study by using the approved ICF. The consent forms must be signed and dated by the subject before any study procedure is initiated.

The Investigator must also explain to any potential subject candidate that they are completely free to refuse to enter the study, or to withdraw at any time without having to give any explanation. The Investigator must further explain to any potential subject candidate that, should they refuse to enter the

study or withdraw from it, their standard of care will not be subject to any change. Patients who decline to participate will not provide any signature.

Each patient will receive a copy of their signed and dated ICF, while the original will be kept with the study records. If applicable, the Investigator or other authorised staff must document the date of informed consent of each subject in the eCRF. Confirmation of informed consent must also be documented in the medical record of the subject.

The ICF should be revised whenever there are changes to the study procedures, in case new safety information changes significantly the risk/benefit assessment or when there is the possibility that such changes may affect the disposition of the subject towards participation in the study. In any of such cases, the ICF should be reviewed, updated, and approved by the EC. To ensure its continued participation to the study, the subject must re-consent to the most updated approved version of the ICF.

